3.2.2 Exclusion Criteria

- 1. Infection of tumor tissue with pathogens resistant to radiation and fungizone
- 2. Patients on systemic immunosuppressive agents, including steroids. Patients who are able to be removed from immunosuppressives at least 5 days prior to the first vaccine will be considered eligible
- 3. Patients with active autoimmune disease or history of transplantation. Patients with indolent or chronic autoimmune disease not requiring steroid treatment are considered eligible.
- 4. Patients who are pregnant or nursing
- 5. Patients experiencing a cardiac events (acute coronary syndrome, myocardial infarction, or ischemia) within the 3 months prior to accrual
- 6. Patients with a New York Heart Association classification of III or IV
- 7. Prior allergic reaction or hypersensitivity to celecoxib or NSAIDs

3.3 Participation of children

Children under the age of 18 years will not be considered as potential candidates because the incidence of peritoneal surface malignancies in the pediatric age group is extremely low and the fact that we do not have data to show that the proposed experimental treatment is feasible and safe to give to children under the age 18 years of age. If new information becomes available to show the proposed treatment has minimal risks when compared to the benefits and is feasible in pediatric patients, the protocol will be amended to include them.

3.4 Women and pregnancy

Because the effect of the proposed investigational treatment was not studied in pregnant women the potential risks to the fetus cannot be assessed, pregnant females will not be included in the study. However, no female of childbearing potential will be excluded from the study. An effective form of contraception of the woman's choice will be required at all times during study. A pregnancy test will be performed on enrolled women of childbearing potential. Should a woman become pregnant or suspect she is pregnant while participating in this study, she should inform her treating physician immediately.

3.5 Minority enrollment

The racial and ethnic characteristics of the proposed patient population will reflect the demographics of Pittsburgh and the surrounding area and/or the patient population of the UPMC Health Systems. We shall attempt to recruit patients in respective proportions to these demographics. No exclusion criteria will be based on race, ethnicity, gender, or socioeconomic status. Patients with immune deficiencies such as human immunodeficiency virus infection will

be excluded. The numbers of enrolled male to female patients will be consistent with and reflective of the numbers of patients seen in the UPMC clinics and in approximate 50:50 proportions. No minorities or their subpopulations will be excluded from the study. Every attempt will be made to encourage participation of minorities in these trials.

4. REGISTRATION PROCEDURES

N/A (Single-Institution Study)

5. TREATMENT PLAN

Prior to starting study treatment patients will undergo CRS + HIPEC surgery. A portion of the resected tumor, removed as part of the patient's clinical care for their disease, will be evaluated for the number of cancer cells as a part of eligibility screening procedures. This tissue will be used to manufacture each patient's autologous vaccine (autologous tumor loaded on the patients' autologous dendritic cells). The beginning of postoperative immunotherapy (defined as week 1) will be based upon recovery from CRS + HIPEC, but no sooner than 6 weeks post-surgery, at the discretion of the investigator/sub-investigator, to allow for adequate recovery from surgery.

Immunotherapy are intended to be administered in the UPCI-CTRC. However, based upon scheduling and logistics those procedures are not limited to UPCI-CTRC and may be administered in equivalent locations at UPMC Shadyside and/or the Hillman Cancer Center.

5.1 Phase 1: Dose assessment of α DC1 vaccine chemokine-modulatory regimen (CKM)

The recommended Phase 2 dose of the combination of α DC1 vaccine in combination with IFN α , rintatolimod, and celecoxib will be established by administering fixed doses of the vaccine, rintatolimod, and celecoxib in combination with escalating doses of IFN α . Patients will receive a priming dose of the vaccine which consists of 1 intranodal injection followed by 1 intradermal injection on the Monday of the first week. Patients will then receive a booster dose of the DC vaccine, which consists of 1 intranodal injection and 1 intradermal injection, on Monday followed by the CKM regimen on days Tuesday through Friday of the booster cycle.

There will be 3 dose finding cohorts with one additional de-escalation cohort (designated -1) if needed, as shown in the table below:

Phase 1 Dose Tiers	α DC1 Vaccine (IN + ID)***	Components of CKM cycle		
		IFN α (MU/M ² IV) Days T-F	Rintatolimod* (mg, IV) Days W&F	Celecoxib** (mg, orally, twice a day) Days T-F
-1	3+3 M cells	5	100	200
1	3+3 M cells	5	200	200
2	3+3 M cells	10	200	200
3	3+3 M cells	20	200	200

*Rintatolimod starting dose will be 200 mg unless dose escalation is from tier -1 in which case cohorts 2 and 3 will use 100 mg of rintatolimod.

**Celecoxib will be administered orally, at a dose of 200 mg, once a day starting the day of the first vaccine (day 1 of week 1) and continue until Friday the last day of the CKM regimen. The dose will be increased to 200 mg, twice a day on the days of vaccination (Monday) and over the 4 days of chemokine modulation regimen (Tuesday - Friday).

***In case of limited availability of vaccine, the treatment may proceed with reduced numbers of the cells (down to 0.5 M IN + 0.5 M ID for each vaccination cycle).

Dose escalation will start with dose tier 1 and proceed to dose tier 2 in the absence of RLTs. Otherwise the dose will be de-escalated to tier -1. The escalation/de-escalation schema uses the following table. Under this schema, more than one patient can be enrolled at the same time; however, *within Phase 1, CKM cannot be started on the next patient until the previous patient completes the cycle of CKM and an additional one week of observation for potential RLTs (total of two week difference between the consecutive patients). Also, CKM cannot be started on the next dose until 2 patients on the lower dose complete the CKM regimen and additional one week of observation for potential RLTs.* Similar rule will be applied during the escalation between different tiers and for the patients within the same dose tier, in order to allow time to evaluate any potential toxicities.

The establishment of the RP2D will be based on an adaptive design for which the next dose will be set according the following rules:

Dose Escalation/De-escalation Rules

Observed Number of RLTs on a Dose Tier	Decision Rule for the Next Subject
There is at least 1 RLT among the last 2 subjects treated on this dose tier and the proportion of DLTs on this dose tier is > 0.30	Assign to next lower dose
There are no RLTs among the last 2 subjects treated on this dose tier and the proportion of RLTs among all subjects on this dose tier is ≤ 0.30	Assign to next higher dose
Neither of the above is satisfied	Assign to the same dose

If no RLTs are observed among the first 3 dose tiers, four additional patients will be added to tier 3 for a total of 6 on tier 3. If, after treating 10 patients without RLT (2 + 2 + 6), dose tier 3 will be declared the RP2D. If an RLT is observed at any dose tier the adaptive up-and-down design will commence until 15 patients are observed after which the Phase 2 starting dose will be estimated by isotonic regression.

Regimen limiting toxicities (RLTs) are defined as the following toxicities:

Vaccine possibly, probably or definitely related RLTs

- Grade 2 or more bronchospasm or generalized urticaria (hypersensitivity)
- Grade 2 or more allergic reaction
- Grade 3 injection site reaction due to vaccine
- > Grade 3 toxicity of any kind related to the DC vaccine

CKM possibly, probably or definitely related RLTs

- Grade ≥ 3 leukopenia or neutropenia persisting ≥ 4 days (96 hours) after treatment
- Greater than or equal to grade 3 non-hematologic adverse events, except for the following grade 3 toxicities unless they last greater than one week:
 - Flu-like symptoms/constitutional symptoms (i.e., fever, chills, arthralgias, myalgias)
 - Depression, anxiety, restlessness, or insomnia
 - Manageable GI symptoms (i.e., nausea, diarrhea)

The observation period for each patient in the Phase 1 portion of this study will be up to 5 weeks (i.e. up to and including the Friday 1 week after the end of the chemokine modulating regimen).

Note: The last 2 patients in the Phase 1 cohort that determines the RP2D will continue on to the Phase 2 part of the trial and will receive the 2nd and 3rd booster/CKM cycles and follow-up per the Phase 2 portion of this protocol. All patients in the dose finding cohort will be followed for primary efficacy endpoints as well as have blood and serum drawn for corollary studies.

Patients in the Phase 1 (safety) cohort will receive their study treatment and will be monitored for RLTs according to the following timeline:

Eligibility	ECOG performance status, blood work CRS + HIPEC
Screening	History and physical exam, ECOG performance status, blood work, and evaluation of tumor material
Post-surgery (after the discharge from the hospital)	Leukapheresis
Week 1* (upon recovery from surgery; at least 4 weeks after surgery)	Priming Vaccine dose; no chemokine modulation Monday: α DC1 vaccine Oral celecoxib, 200 mg, twice daily on the day of vaccination Tues – Sun: oral celecoxib 200mg, once daily
Weeks 2-3	Rest – continue oral celecoxib, 200 mg, once daily
Week 4	Cycle 1 (“booster cycle”) Monday: α DC1 vaccine Tues – Fri: Systemic Chemokine Modulation Regimen. Oral celecoxib, 200 mg, twice daily on the days of vaccination and CKM. Celecoxib will be discontinued after CKM on Friday. Rintatolimod is only administered on Wednesday and Friday.
Off study treatment	Follow-up for Time-to-Progression/occurrence (TTP)

CRS: Cytoreductive surgery; HIPEC: Hyperthermic intraperitoneal chemoperfusion; TTP: Time-to-progression

*Adjuvant immunotherapy may be delayed until full recovery at the discretion of the investigator/sub-investigator. The beginning of immunotherapy will be considered week 1 of the experimental treatment and the timing of all subsequent elements of treatment will be based upon the first vaccine.

5.2 Phase 2: Efficacy assessment of α DC1 vaccine followed by the chemokine-modulatory regimen (CKM)

Study treatment will consist of one priming dose of DC vaccination followed by 3 booster cycles of DC vaccine + chemokine modulation regimen (CKM), cycles 1-3. The booster vaccine is administered on Monday followed by 4 days of the CKM regimen (Tuesday – Friday).

Timing of the experimental treatment:

- Priming cycle: 6 to 16 weeks after surgery (target: 8 weeks)
- Booster cycle 1: 4 to 12 weeks after priming cycle (target: 4 weeks)
- Booster cycle 2: 4 to 12 weeks after booster cycle 1 (target: 4 weeks)
- Booster cycle 3: 4 to 12 weeks after booster cycle 2 (target: 4 weeks)

It is expected that a significant proportion of the patients will undergo adjuvant clinically indicated chemotherapy. Adjuvant chemotherapy can be administered between the courses of immunotherapy, but no sooner than 5 days after finishing any cycle of immunotherapy. The following cycle of immunotherapy will start no sooner than 5 days after the last day of a chemotherapy cycle and after recovery from acute side effect of chemotherapy.

Patients who (for clinical or logistic reasons) will not be able to take any cycle of immunotherapy within the above-indicated windows, can still receive the remaining courses of immunotherapy at later time points, but will not be included in the analysis of the primary efficacy endpoint, although they can be analyzed in an exploratory manner.

Similarly, patients who (for clinical or logistic reasons) will not be able to receive the priming dose of vaccine within 3 months after surgery, can still receive immunotherapy at later time points, but will not be included in the analysis of the primary efficacy endpoint, although they can be analyzed in an exploratory manner.

In the efficacy phase, patients will receive a priming dose of the α DC1 vaccine followed by 3 courses of the α DC1 booster vaccine combined with CKM regimen as illustrated in the following table:

Eligibility	Informed Consent CRS + HIPEC
Screening	History and physical exam, ECOG performance status, blood work, evaluation of tumor material
Post-surgery (within the first 8 weeks following surgery)	Leukapheresis
Week 1* (upon recovery from surgery; no sooner than 6 weeks post-surgery)	Priming Vaccine dose; no chemokine modulation) One day: α DC1 vaccine Oral celecoxib, 200 mg, before and after treatment on the day of vaccination
Weeks 2-3	Rest
Week 4 (target)*	Booster Cycle 1 Monday: α DC1 vaccine

	Tues – Fri: Systemic Chemokine Modulation Regimen. Oral celecoxib, 200 mg, twice daily on the days of vaccination and CKM. Celecoxib will be discontinued after CKM on Friday. Rintatolimod is only administered on Wednesday and Friday.
Week 5-7	Rest
Week 8 (target)**	Booster Cycle 2 Monday: α DC1 vaccine. Reintroduce oral celecoxib, 200 mg, twice daily on the days of vaccination and CKM. Tues – Fri: Systemic Chemokine Modulation Regimen. Rintatolimod is only administered on Wednesday and Friday. Celecoxib will be discontinued after CKM on Friday.
Week 9-11	Rest
Week 12 (target)**	Booster Cycle 3 Monday: α DC1 vaccine. Tues – Fri: Systemic Chemokine Modulation Regimen. Rintatolimod is only administered on Wednesday and Friday. Oral celecoxib, 200 mg, twice daily, will be given on the days of vaccination and CKM. Celecoxib will be discontinued after CKM on Friday.
Off study treatment	Follow-up for Time-to-Progression/occurrence (TTP)

CRS: Cytoreductive surgery; HIPEC: Hyperthermic intraperitoneal chemoperfusion; TTP: Time-to-progression

*Adjuvant immunotherapy may be delayed until recovery at the discretion of the investigator/sub-investigator. The beginning of immunotherapy will be considered week 1 of the experimental treatment and the timing of all subsequent elements of treatment will be based upon the first vaccine.

**Patients may receive postoperative (standard of care, adjuvant) chemotherapy at the discretion of the treating oncologist. Adjuvant chemotherapy may start 5 days after the first full cycle of immunotherapy (first booster vaccine + CKM). Following completion of adjuvant chemotherapy, subsequent immunotherapy can start after 5 days post adjuvant chemotherapy.

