6. DOSING DELAYS/DOSE MODIFICATIONS

Each vaccination and/or chemokine-modulation regimen may be delayed for up to 8 weeks and all subsequent cycles will be adjusted accordingly.

6.1 Phase 1

Any patient who experiences a RLT will be removed from study treatment and followed until the RLT resolves to Grade 1 or baseline.

6.2 Phase 2

After cycle 1, any AE experienced by a patient must resolve to Grade 1 or baseline prior to receiving adjuvant chemotherapy.

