13.4 Continuous Safety Monitoring During the Efficacy Phase

We will use continual Bayesian monitoring of treatment-related regimen limiting toxicities with a stopping rule that permits suspension of the trial by the investigator for review by the Data

Safety and Monitoring Committee (DSMC). We have selected a moderately vague prior probability of an RLT to conform to our prior beliefs that the probability of an RLT is unlikely to be greater than the 30% target of the dose finding phase and could be lower if no RLTs are found in Phase 1. Specifically we chose a beta prior distribution with parameters $a = 1.93$ and $b = 4.74$ which yields a distribution with a mode of .2, a mean of .29.

A stopping rule will be based on the updated posterior probability of an RLT. If the posterior probability exceeds .80 that 30% or more of the patients experience a treatment-related RLT, the study will be suspended pending review by the DSMC. In order to permit continuous monitoring of serious patient toxicities, the following table was prepared based upon cumulative observed AEs at any point in the trial and can be used to signal when either arm should be suspended and reviewed by the DSMC. Values are presented in the table in intervals of 5 or 10 patients

Number of RLTs needed to suspend the trial

Number of Patients	RLTs	$P(\pi R > .30)^*$	$B(RLT)^{**}$
5	4	0.927	0.031
10	5	0.831	0.15
15	7	0.857	0.131
20	9	0.879	0.113
25	10	0.812	0.189
30	12	0.841	0.159
35	14	0.865	0.135
40	15	0.812	0.193
45	17	0.839	0.164
50	19	0.862	0.141
60	22	0.842	0.162
70	25	0.826	0.18
80	28	0.811	0.195
90	32	0.854	0.15
100	35	0.842	0.163
110	38	0.832	0.174
120	41	0.822	0.184
130	44	0.813	0.194
140	47	0.805	0.202
150	51	0.842	0.163
160	54	0.834	0.171
168	56	0.812	0.194

* $P(\pi|R > .30)$ = Posterior probability of a treatment-related RLT exceeds 30% given R, the number of observed RLTs and the prior distribution.

** $B(RLT)$ is the binomial probability of observing at least the number of RLTs in column 2 if the underlying rate of RLT is 30%.

This table presents the minimum number of RLTs that dictate suspension of the trial in accordance with the stopping rule. For example, according to this table 5 RLTs among any of the

UPCI #: 12-110

Version Date: 03-18-2016

first 10 enrolled patients on the efficacy phase will trigger suspension of the trial.

REFERENCES

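### Phase 1 row 2 escalates on the current tier's tally alone, so new patients can be sent to tier 2 or 3 at 3/3 RLTs or worse with no numeric trigger for DSMC review (low-priority safeguard)

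*Combined protocol and SAP*

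**What the plan says.** Section 5.1 sets each Phase 1 assignment by a three-row table, and every row is worded for the tier the last patient was on.

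- **Row 1** moves down if there is an RLT among the last two patients on the tier and the tier's proportion is above 0.30. (It prints DLTs for the proportion; I read RLTs.)
- **Row 2** moves up if the last two patients on the tier had none and "the proportion of RLTs among all subjects on this dose tier is ≤ 0.30".
- **Row 3** otherwise stays.

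On duration: "If an RLT is observed at any dose tier the adaptive up-and-down design will commence until 15 patients are observed". On timing: "CKM cannot be started on the next dose until 2 patients on the lower dose complete the CKM regimen", with a further week of observation. The text adds that a similar rule holds when escalating between tiers.

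The rintatolimod footnote sets the dose at 200 mg "unless dose escalation is from tier -1 in which case cohorts 2 and 3 will use 100 mg of rintatolimod".

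When an RLT occurs in Phase 1, section 6.1 acts on the patient: "Any patient who experiences a RLT will be removed from study treatment". Section 13.4 has a numeric rule. It tracks the posterior for the RLT rate, and when this "exceeds .80 that 30% or more of the patients experience a treatment-related RLT, the study will be suspended pending review by the DSMC". Its heading, its worked example and section 5.6 all place that rule in the efficacy phase. Section 12.1 provides monthly DSMB meetings, with summaries going to a DSMC that also meets monthly. Either body may suspend accrual.

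**The concern.** The decision to move up uses only the lower tier's record. Suppose tier 3 has been tried, produced RLTs and been left. Once the lower tier again satisfies row 2, the next new patient goes back to tier 3, whatever tier 3's tally is. The same holds for tier 2 seen from tier 1. The cycle can repeat until 15 patients have been observed.

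What is at stake is the safety of the few patients assigned to a tier that already looks clearly toxic. The isotonic fit that sets the Phase 2 dose comes only after the last of them has been treated, so it cannot protect them.

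**Working it through.** **Inputs.** Table rows, 15-patient limit and two-patient stagger: section 5.1. Prior Beta(1.93, 4.74), 30% reference rate and suspension table: section 13.4. The protocol gives no true RLT rates; those below are assumptions.

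**1. Reproduce the plan's figures.** With r RLTs in n patients, the posterior is Beta(1.93 + r, 4.74 + n − r), and the quantity tabled is its tail above 0.30. For 5 of 10, Beta(6.93, 9.74) gives 0.831, and the binomial chance of at least 5 of 10 at 30% is 0.150. The plan prints 0.831 and 0.15. All 22 printed rows reproduce.

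**2. Apply the same formula to one tier's tally.**

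| Tally | Tail above 0.30 |
|---|---|
| 1/1 | 0.659 |
| 1/2 | 0.562 |
| 2/3 | 0.740 |
| 2/2 | 0.816 |
| 3/4 | 0.858 |
| 3/3 | 0.908 |
| 4/5 | 0.927 |
| 4/4 | 0.957 |
| 5/5 | 0.981 |

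A posterior above 0.90 is first met at 3 of 3, 4 of 4 or 4 of 5.

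**3. Trace the worst case.** Tiers 1 and 2 are always clean and tier 3 is always toxic (x = RLT). Row 2's last two patients can be read in two ways.

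- *Reading A: two new patients are needed on each visit before moving up.* Tiers: 1, 1, 2, 2, 3x, 2, 2, 3x, 2, 2, 3x, 2, 2, 3x, 2. Tier 3 gets 4 of 15 patients, the last assigned at 3/3.
- *Reading B: earlier patients on the tier count.* Tiers: 1, 1, 2, 2, 3x, 2, 3x, 2, 3x, 2, 3x, 2, 3x, 2, 3x. Tier 3 gets 6 of 15 patients, three of them assigned at 3/3, 4/4 and 5/5.

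If assignment to tier 3 is held once it stands at 3/3, and the DSMC does not agree to reopen it, tier 3 gets 3 patients on either reading. With tier 1 clean and tier 2 always toxic, the returns to tier 2 run up to 4/4 (A) and 6/6 (B). That these tallies can be reached does not depend on any assumed rate.

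**4. Would the 13.4 rule, pooled over tiers, catch this?** No. The reading B path ends at 6 RLTs in 15 patients, and the 13.4 table needs 7 of 15.

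**5. How often.** The rows were simulated patient by patient (20,000 trials per case), with assumed rates of 2/5/10% on tiers -1/1/2 and the 100 mg footnote ignored. Share of trials with at least one return to tier 2 or 3 at posterior above 0.90:

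| True tier 3 rate | Reading A | Reading B |
|---|---|---|
| 80% | 24% | 50% |
| 60% | 10% | 24% |
| 40% | 3% | 7% |
| 30% | 1% | 3% |
| 20% | 0.4% | 1% |

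With 2/5/5/10% on tiers -1/1/2/3, returns even at posterior above 0.80 occur in under 2% of trials.

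**The case against.** **Revisiting tiers is what an up-and-down design does.** This stands. Section 13.4 speaks of "the probability of an RLT is unlikely to be greater than the 30% target of the dose finding phase", so 30% is a target and not a ceiling. Returns at 1/1, 1/2 or 2/3 are normal. A reader might infer that any return to a tier above 30% is a fault; the documents do not support that. Row 1 also steps down after each RLT while the tier stands above 0.30.

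**Phase 1 is not unsupervised.** A reader might infer that it is. Section 12.1 covers it with monthly review and authority to suspend accrual, and section 5.1 staggers patients ("total of two week difference between the consecutive patients"), so a review falls about every two patients. What is missing is only a count that prompts action.

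**13.4 is a different rule.** It pools patients on the efficacy phase at one chosen dose, and its table starts at 4 of 5. A reader might infer that Phase 1 breaches it at 2/2, where 0.816 narrowly passes 0.80. It does not, because the rule does not apply there. Two of two is also weak evidence: at a true rate of exactly 30% its chance is 0.3 × 0.3 = 0.09, against 0.3 × 0.3 × 0.3 = 0.027 for three of three.

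**Reading A is better supported.** The stagger sentence and the statement that a similar rule applies between tiers favour it, so the lower figures deserve more weight.

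**The toxic case is unlikely.** Section 2.6.3 reports a sister trial with the same IFN doses and daily rintatolimod that had no RLTs in its Phase 1. This is real reassurance, but that section describes chemokine modulation with no mention of the vaccine, and vaccine-related events count as RLTs here.

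**Conclusion.** The gap is real and small. The written rule can assign new patients to tier 2 or 3 at 3/3, 4/4 or 5/5, and the plan names no count that would bring the DSMC in during Phase 1. That follows from the text alone.

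The frequencies rest on the assumed rates and on the reading of the last two subjects. The effect is material only if a tier is clearly toxic: 24% to 50% of trials at a true 80%, against about 1% to 3% at 30% and 0.4% to 1% at 20%.

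The point does not cover tier -1, which has no lower dose, or re-entry to tier 1, which the rintatolimod footnote may exclude. It would be tempting to conclude that the recommended Phase 2 dose is compromised. The calculations do not show that; this is mainly about patient exposure during Phase 1. It is a cheap patient-safety improvement, of low priority.

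**What to change.** Add to row 2: *If the next higher tier (2 or 3) has already been opened and the posterior probability that its RLT rate exceeds 30% is above 0.90 (prior as in 13.4; first met at 3 of 3, 4 of 4 or 4 of 5), assign to the same dose and do not return to the higher tier until the DSMC has reviewed it and agreed.* Count the 100 mg and 200 mg rintatolimod versions of a tier separately, since they are different regimens. In the same edit, state whether the last two subjects may include patients treated before a return to the tier.

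This is a new, tier-specific rule; copying 13.4 in its pooled form would not do the job.

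**Cost.** No extra patients and no halt to accrual, because patients continue at the lower tier. The price is an occasional DSMC review and up to a month at that tier, or about two patients at two-week spacing. At a true tier 3 rate of 20% to 30% the gate fires in about 0.4% to 3% of trials, with no loss in the chance of selecting tier 3 beyond simulation error.

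**Option.** A trigger at 0.80 (from 2 of 2) saves more RLTs if tier 3 is very toxic. It fires in 8% to 12% of trials at a true 30%, however, and can cost about 2 to 4.5 percentage points of tier 3 selection, depending on the reading, the tie-break in choosing the dose and the DSMC's response. I would use 0.90.

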7.1 Adverse Events and Risks List(s)

7.1.1 DC Vaccine

Dendritic cell vaccines have been investigated extensively in a number of centers and to date, have not been reported to be associated with limiting toxicities or adverse side effects. DC vaccines carry a potential risk of development of autoimmune disease (such as lupus, or vitiligo). Whereas development of vitiligo has been reported with similar vaccines administered to melanoma patients (and correlated with positive response to vaccination), other side effects have not been reported. Although, based on previous trials with DC-based vaccines, the possibility of developing an allergic reaction to DC-based vaccines is rare there is a chance that patients could have an allergic reaction to the vaccine.

While other classes of immunotherapeutic drugs, particularly the currently approved immune checkpoint blocker, Yervoy [Ipilimumab] can produce significant toxicity, such as enterocolitis, hepatitis, dermatitis (including toxic epidermal necrolysis), neuropathy, and endocrinopathy, due to its ability to promote polyclonal T-cell activation and proliferation, such effects have not been described following application of DC cancer vaccines, including previously-administered alpha-DC1-based vaccines, their combinations with a long acting TLR3 ligand poly-ICLC (Okada,

Kalinski, Bartlett, J. Clin. Onc. 29 (3):330-336, 2011) or their combinations with the proposed CKM regimen in our patients treated on compassionate-use protocols.

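### Grade 3 toxicity attributed only to the vaccine, other than allergic or injection site reactions, is outside the RLT definition and so outside the Phase 1 tally and the Phase 2 stopping rule

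*Combined protocol and SAP*

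**What the plan says.** Section 5.1 has two RLT lists. The vaccine list has four items: "Grade 2 or more bronchospasm or generalized urticaria (hypersensitivity"), "Grade 2 or more allergic reaction", "Grade 3 injection site reaction due to vaccine" and "> Grade 3 toxicity of any kind related to the DC vaccine". Section 6.2.1 gives the same four items as grounds for removing a patient from treatment in Phase 2.

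The second list is headed "CKM possibly, probably or definitely related RLTs". It contains "Grade ≥ 3 leukopenia or neutropenia persisting ≥ 4 days (96 hours) after treatment" and "Greater than or equal to grade 3 non-hematologic adverse events". The non-hematologic item exempts grade 3 flu-like or constitutional symptoms, mood and sleep symptoms, and manageable GI symptoms, unless they last more than a week.

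In Phase 1 the RLT count decides escalation and de-escalation, and ten patients without an RLT make tier 3 the recommended Phase 2 dose. In Phase 2, section 13.4 monitors treatment-related RLTs against a table of 22 boundaries. It gives no new definition, so the section 5.1 definition carries over.

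On expected vaccine toxicity, section 7.1.1 states "DC vaccines carry a potential risk of development of autoimmune disease (such as lupus, or vitiligo"). It adds that DC vaccines have not so far been associated with limiting toxicity.

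**The concern.** The two lists treat events of the same grade differently according to attribution. A grade 3 autoimmune event judged at least possibly related to CKM is an RLT. The same event judged related to the vaccine alone is not, although a grade 3 reaction at the injection site is. The plan gives no reason for the difference, and the excluded class contains the one systemic risk, apart from allergy, that section 7.1.1 names for the vaccine.

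Safety is part of the primary objective (section 1.1). If such events occur, the Phase 1 tally and the 13.4 table can read low while severe toxicity of the tested product accumulates. The grade 3 hold-and-reduce rule in 6.2.2 does not close the gap, because it covers CKM only.

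**Working it through.** **Which grade 3 events count (section 5.1)**

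| Grade 3 event | RLT? |
|---|---|
| Vaccine-related allergic reaction, bronchospasm or generalized urticaria | Yes, from grade 2 |
| Vaccine injection site reaction | Yes |
| Non-hematologic, at least possibly CKM-related | Yes, apart from the short-duration exemptions |
| Leukopenia or neutropenia, at least possibly CKM-related | Only if it persists 4 days or more |
| Any other event attributed to the vaccine only | No |

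The last row is the gap. A misprint for at-least-grade-3 cannot be excluded, but the strict sign is printed in both 5.1 and 6.2.1. The separate grade 3 injection site item would also be redundant under the wider reading. The literal reading is therefore the better supported one.

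**The plan's own table (section 13.4)**

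Inputs: prior Beta(1.93, 4.74); suspend when the posterior probability that the RLT rate exceeds 0.30 is above 0.80. With r RLTs in n patients, the posterior is Beta(1.93 + r, 4.74 + n − r).

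- n = 10, r = 5: Beta(6.93, 9.74), tail above 0.30 = 0.831 (printed 0.831). With r = 4 it is 0.667, so 5 is the minimum.
- n = 168, r = 56: Beta(57.93, 116.74), tail = 0.812 (printed 0.812). With r = 55 it is 0.765.
- The binomial tails at a 30% rate are 0.150 and 0.194 (printed 0.15 and 0.194).

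All 22 rows reproduce in both probability columns, and each count is the true minimum. The prior mode is 0.93/4.67 = 0.199 and the mean 1.93/6.67 = 0.289, as stated. The table is sound; the issue is which events feed it.

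**Effect on the chance of suspension**

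The documents give no rate for the uncounted events, so these rates are assumptions. Let c be the proportion of patients with a counted RLT and u the further proportion with only an uncounted grade 3 vaccine event. As written, the rule sees rate c; if those events were counted, it would see c + u. The probability of reaching any of the 22 boundaries by 168 patients was computed exactly. Binomial distributions were convolved from look to look, removing paths that had reached a boundary. Patients are taken as independent with a constant rate.

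| c | u | c + u | Suspension as written | Suspension if counted |
|---|---|---|---|---|
| 20% | 1% | 21% | 5.6% | 7.1% |
| 20% | 2% | 22% | 5.6% | 9.1% |
| 20% | 5% | 25% | 5.6% | 18.2% |
| 20% | 10% | 30% | 5.6% | 49.6% |
| 10% | 3% | 13% | 0.2% | 0.7% |
| 10% | 5% | 15% | 0.2% | 1.4% |

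**Phase 1**

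The chance of no RLT in ten patients, with an assumed 5% counted rate at every tier, is 0.95^10 = 0.60. If a further 5% were counted it would be 0.90^10 = 0.35.

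**The case against.** The strongest reply is that the gap is narrow and not left to chance, and that a threshold specific to each component may be deliberate. Several parts of this stand, and they rule out stronger readings that a reader might infer.

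- *That all grade 3 systemic vaccine toxicity escapes.* It does not. Allergic reaction, bronchospasm and generalized urticaria are systemic and count from grade 2.
- *That every event between priming and the first CKM cycle escapes.* It does not. Celecoxib is a CKM component and is given around priming, so an event judged possibly related to it can fall under the CKM list.
- *That such an event leads to no action.* Section 5.7 allows removal for unacceptable adverse events, section 6 allows a vaccination to be delayed, and section 6.3 withholds protocol drugs for persistent GI toxicity. Section 12.1 provides monthly DSMB review, with both DSMB and DSMC able to suspend accrual. Section 13.3 summarizes all adverse events by grade and attribution. None of these is a numerical trigger.
- *That the stopping rule is largely disabled.* Assuming 20% counted plus 15% uncounted gives 5.6% against 86.0%, but nothing in the documents supports a 15% rate, and section 7.1.1 points to low vaccine toxicity. At 1% to 2% the change is small.

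The Phase 1 consequence is also limited. The target vaccine dose is the same in every tier and interferon is what is escalated, so a vaccine-only event says little about which tier is tolerable.

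What the reply does not supply is a stated reason why a grade 3 local reaction counts and a grade 3 autoimmune event does not, or a numerical rule that would register the latter.

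**Conclusion.** The point holds in a limited form. As printed, a grade 3 event attributed only to the vaccine, other than an allergic or hypersensitivity reaction or an injection site reaction, is not an RLT. It is missing from the Phase 1 tally and from the only prespecified numerical stopping rule in Phase 2. Discretionary safeguards remain.

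The existence of the gap follows from the text alone. Its size does not: it depends on how often such events occur and how they are attributed, which the documents do not say. With 20% counted RLTs the effect runs from minor (1% to 2% uncounted) to material (5% to 10% uncounted). The documents do not settle whether the strict inequality is intended or a misprint; either way it needs correction or a stated justification.

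**What to change.** Reconcile the vaccine and CKM grade thresholds in sections 5.1 and 6.2.1. The sponsor and the DSMC should confirm whether the strict inequality is intended, give the reason if it is, and decide the threshold; none is proposed here. State in 13.4 that the reconciled definition is the one counted.

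Until that is done, report to the DSMC, beside the 13.4 count, the number of patients with a grade 3 vaccine-attributed event that was not counted as an RLT. Keep the section 5.1 exemptions for short flu-like, mood or sleep, and GI symptoms. Do not apply the 13.4 boundaries to a broader event such as every grade 3 or higher treatment-related event: they are set against a 30% RLT rate, and a broader event occurring in 40% of patients (an assumption) would reach a boundary with probability of about 99%.

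The cost is a few words in 5.1, 6.2.1 and 13.4 and one extra line in the safety report. If the reconciliation widens the definition, slightly more RLTs may be counted.
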